Official title: Scrambler therapy improves pain in neuromyelitis optica: a randomized controlled trial

NCT: NCT03452176

Document date: November 13, 2019

Standard protocol approvals, registrations, and patient consents:

We enrolled 22 patients with NMOSD (11 per arm) at the Johns Hopkins Neuromyelitis Optica Clinic. Participants with severe limitations to mobility or sight due to their disease were given the option to have study visits conducted in their homes. The protocol was approved through the Johns Hopkins Institutional Review Board (IRB00115699) and launched on March 2, 2018. Written informed consent was obtained from each participant prior to study enrollment. The study was registered through ClinicalTrials.gov (NCT03452176). The Food and Drug Administration granted Scrambler therapy (FDA) 510(k) approval for acute, chronic and post-operative pain, "Scrambler ST 5 TENS Device," (K081255) in February 2009.

Participants:

Participants with self-reported neuropathic pain caused by NMOSD were recruited through the Johns Hopkins Neuromyelitis Optica Clinic. For participation eligibility, patients were aged 18 years or older with an NMOSD diagnosis based on the 2015 international consensus diagnostic criteria,²⁰ regardless of anti-aquaporin 4 (AQP4) serostatus. For inclusion, neuropathic pain needed to be attributable to an inflammatory spinal cord lesion, indicated by MRI from a previous clinical myelitis event. Persistent pain needed to be rated at a level of 4 or higher on an 11-point numeric rating scale (NRS), with persistent pain defined by presence for >3 months. Patients needed to be stable in their disease, such that they had no spinal cord relapses within 6 months prior to enrollment. Patients were eligible to use any combination of standard of care medications for pain treatment, including anti-epileptic, antidepressant, opioid or non-steroidal

anti-inflammatory medications, with no adjustments to the regimen within 30 days of enrollment. Patients with a known or suspected concomitant diagnosis of peripheral neuropathy were excluded. Patients with an ongoing concomitant central neurologic disorder were excluded, as were those who used an investigational agent for pain control within 30 days of enrollment, were pregnant or breastfeeding, were cognitively or mentally incompetent, or had implantable pain management or arrhythmia devices.

Randomization and Masking:

Following consent and screening, participants were randomly assigned to receive Scrambler treatment versus sham at a 1:1 ratio for 10 consecutive weekdays. Recruitment was batched using a randomized block design stratifying across medication class (anti-epileptic, antidepressant, opioid or none) and pain level at screening (moderate 4-6, or severe 7-10) to promote similar distributions across groups in this small study. The rationale was to increase homogeneity between groups due to limited data that suggest response to Scrambler therapy may differ due to interference of medications used for pain.²³ Randomization assignments were assigned by a third-party utilizing www.randomizer.org.

Scrambler therapy was administered via the GEOMC Pain Scrambler, model MC-5A. Electrodes were placed on participants receiving treatment within the dermatome above and below the level of injury, in a sufficiently sensitive area closest to the pain. For instance, if the patient had pain in the back from C3 to C8, a set of electrodes would be placed at C2 (above the pain) and T1 (below the pain.) Stimulation intensity was increased until a maximum tolerable threshold

was reached without being painful, per the established protocol. If the patient felt a constant burn, sting or feeling of discomfort, electrodes were repositioned. The exact electrode positioning depended on the demarcation of the surface pain area, and analgesic response of the patient. Once the channel was regulated to the patient's maximum intensity, pain was assessed by asking the patient how s/he felt in the area of pain covered by the electrodes and adjusted for desired effect of reduced pain and/or analgesic response. Additional channel-pairs were similarly implemented as necessary based on size of pain area, up to 5 pairs in total. Electrodes remained in the established position and intensity for 35 minutes from the time of proper placement was instituted. As central pain is often more pervasive as compared with peripheral neuropathy, more than one area was often targeted.

For the sham group, small motors (<1 cm) which produce a vibratory sensation similar to a wearable activity tracker (i.e., FitBit) were connected to each electrode to simulate Scrambler stimulation but without electrical charge. Channel-pairs were similarly applied in a sufficiently sensitive dermatome closest to the pain, surrounding the level of spinal cord injury. The sham sensation was applied for 35 minutes.

For both groups, the Scrambler machine was kept behind a curtain to help preserve masking. The machine itself was turned on for all participants, though without emitting any stimulation in those receiving sham, so that the alert indicating termination of treatment would be heard by all participants regardless of treatment assignment. Because treatment effect has been shown to vary across technicians, one technician was trained in the proper delivery of Scrambler treatment and performed all interventions.

Study objectives and measures:

Our primary objective was to test the hypothesis that Scrambler therapy is an effective, acceptable, feasible and safe treatment of persistent central neuropathic pain for patients with NMOSD. To test this hypothesis, we performed a randomized single blind, sham-controlled trial testing Scrambler therapy in patients with NMOSD. The primary outcome was feasibility and acceptability. Secondary endpoints included both safety and effectiveness at the end of the 10-day treatment period. Feasibility of treatment was examined to determine whether the intervention was appropriate for this patient population, toward the effort of informing a larger, Phase III study. This was measured by assessing the following: 1) adherence to visit schedule and 2) response to the following question asked directly after completion of the 10-day treatment period: "Do you think you received treatment?" (Yes/No). Acceptability was measured by assessing response to the following question, also asked directly following the treatment course: "Would you want to continue treatment in clinic, if available?" (Yes/No).

Safety of the intervention was evaluated by comparing Adverse Events (AEs) and Serious Adverse Events (SAEs) in the treated versus sham groups. These were monitored and documented prior to initiation of each treatment daily, at termination of final treatment, and at 30- and 60-day follow-up.

Effectiveness was evaluated based on degree of improvement in pain, comparing the treatment group to sham. Prior to initiation of Scrambler therapy and at completion of treatment, patients were asked to rate their pain by the 11-point NRS score. Patients additionally reported NRS pain

scores at 30- and 60- days following therapy completion to assess sustainability of treatment effect.

Although not powered appropriately, an exploratory objective aimed to assess the relationship between improved pain and other co-occurring symptoms. Prior to initiation of Scrambler therapy, patients were asked to complete each of the following measurement tools to determine baseline pain severity and interference, anxiety, depression, and sleep disturbance, respectively: Brief Pain Inventory (BPI), Neuro-QoL [Quality of Life in Neurological Disorders] Short Form v1.0 - Anxiety, Neuro-QoL Short Form v1.0 - Depression, and Neuro-QoL Short Form v1.0 - Sleep Disturbance. Measurement tools were accessed by participants via a secure online portal. Participants were provided with an alphanumeric code that enabled their responses to be linked to their demographic and clinical data in a confidential manner. Questionnaires were mailed to participants without internet access with a postage-paid envelope provided for return of questionnaires. Patients again completed all measurement tools at end of treatment, and at 30- and 60-days following end of treatment.

Statistical analysis:

As one measure of feasibility of treatment, adherence to visit schedule was ascertained. We report the number of patients in each group who were able to complete all treatments. Fisher's exact test was performed to assess if adherence is independent of group assignment. For each of the two survey questions used to assess feasibility and acceptability, as described above, a 95% confidence interval for the proportion of participants answering "Yes" was calculated.

Given the small number of patients in the study, exact binomial confidence intervals were calculated since normal distribution could not be assumed.

Descriptive statistics were used to report AEs and SAEs. Incidence and severity were compared between groups.

Effectiveness was based on degree of improvement of pain and compared NRS pain scores in the treatment group and sham group using the Friedman One-Way Repeated Measure Analysis of Variance by Ranks test at baseline, following treatment, and at 30- and 60-day follow-up.

Wilcoxon signed-rank testing was used to determine sustainability over time by comparing scores at baseline to those following treatment, at 30-day follow-up and at 60-day follow-up. A chi-squared analysis comparing the number of treated patients who thought they received treatment versus the number of sham patients who thought they received treatment was performed to determine if masking was effective.

The target sample size of 22 (11 per arm) was based on previous studies which suggest that the average pain value at baseline is at least 4 on the 0-10 NRS with a standard deviation of the original pain value expected to fall in the range of 1-1.5 in this patient population. A conservative estimate of the standard deviation of the change across patients from Day 1 to Day 10 was approximately up to 2. With 11 patients in each arm and under these assumptions, we were able to detect a change of 2.5 points in the Scrambler group at 80% power, with a difference in proportions of 60% between the two groups.

To explore the impact on co-occurring symptoms when intervening on pain, scores were tabulated for each of the following based on measurement tool data: anxiety, depression, sleep

disturbance and pain interference. Friedman One-Way Repeated Measure Analysis of Variance by Ranks was tabulated for each symptom, comparing the change at baseline, following treatment, and at 30- and 60-day follow-up timepoints in each arm. A subanalysis was similarly conducted in those patients who “responded” to Scrambler treatment versus sham. Based on a cohort of adult patients with spinal cord injury who reported clinically meaningful change in pain over time, “response” was defined as patients with a decrease in NRS pain scores of 1.80 points between baseline and end of treatment.

Demographic and clinical characteristics were compared between Scrambler and sham groups using Mann-Whitney *U* and Chi-squared testing, as appropriate.

Data availability:

Public Law 110-85 (also known as the FDA Amendments Act of 2007) mandates registration and results reporting of "applicable clinical trials" in ClinicalTrials.gov. We support efforts to promote data sharing toward the advancement of science and registered this clinical trial, providing trial design, eligibility criteria and outcomes measures.

Classification of evidence:

This study provides Class II evidence of Scrambler therapy use in patients diagnosed with NMOSD who have central neuropathic pain.

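### The pain comparison between Scrambler and sham uses neither the stratification factors nor baseline NRS as a covariate, so available precision goes unrecognised (a modest point on a secondary endpoint)

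*Combined protocol and SAP*

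**What the plan says.** Under Randomization and Masking, participants were allocated 1:1 using a "randomized block design stratifying across medication class (anti-epileptic, antidepressant, opioid or none) and pain level at screening (moderate 4-6, or severe 7-10"). The stated purpose was "to promote similar distributions across groups in this small study", and the stated reason was "limited data that suggest response to Scrambler therapy may differ due to interference of medications used for pain". The Participants section adds that "Patients were eligible to use any combination of standard of care medications for pain treatment", so the listed classes can overlap.

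Under Study objectives and measures, NRS is recorded before treatment, at its completion, and 30 and 60 days later. Effectiveness is a secondary endpoint.

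Under Statistical analysis, the pain analyses are:
- a Friedman test over the four time points;
- Wilcoxon signed-rank tests of each later score against baseline;
- a responder subanalysis defined by a fall of 1.80 points from baseline.

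None of these carries a term for medication class or pain band. The only use of baseline characteristics across arms is a set of tests: "Demographic and clinical characteristics were compared between Scrambler and sham groups using Mann-Whitney" U and chi-squared procedures.

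**The concern.** The design treats pain level and medication as important enough to stratify on, but the analysis then ignores them. Two things follow for any unadjusted between-arm comparison of pain.

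First, if the factors are prognostic, balancing them lowers the true variance of the treatment difference. The usual standard error does not know this and is too large, so the test is conservative.

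Second, a change score removes an additive baseline difference in full, which is right only if the slope of end score on baseline is 1. With a smaller slope, patients selected at NRS 4 or more regress toward the mean, and part of any chance baseline difference remains in the contrast.

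Testing baseline characteristics between arms corrects neither problem, and with 11 per arm a non-significant result does not show balance. With 22 patients, baseline NRS is a cheap possible source of precision for the outcome on which the sample size rests.

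**Working it through.** **Inputs from the document** (Statistical analysis, sample-size paragraph): 11 per arm, baseline SD s0 of 1 to 1.5, SD of change up to about 2, a 2.5-point change, 80% power. **Assumed**, because not stated: a two-sided 5% test and the baseline-to-end correlation ρ.

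**1. The plan's own figure.** For an unadjusted t-test on change, SE = 2 × √(2/11) = 0.853 and the noncentrality is 2.5/0.853 = 2.93. With 20 df, power is 79.6%, which reproduces the stated 80%. A paired test within the Scrambler arm alone would give 96.1%. The stated power therefore matches an unadjusted between-arm comparison of change.

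**2. Baseline NRS as covariate.** Keep the SD of change at 2 and find the end-of-treatment SD s1 from s0² + s1² − 2ρ·s0·s1 = 4. The residual SD is s1·√(1 − ρ²). The SE is residual SD × √[(2/11)(1 + 1/18)], with 19 df. The slope of end score on baseline is ρ·s1/s0.

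| s0 | ρ | s1 | slope | residual SD | power |
|---|---|---|---|---|---|
| 1.5 | 0.11 | 1.50 | 0.11 | 1.49 | 95.2% |
| 1.5 | 0.3 | 1.85 | 0.37 | 1.76 | 86.7% |
| 1.5 | 0.5 | 2.27 | 0.76 | 1.97 | 78.6% |
| 1.5 | 0.6 | 2.50 | 1.00 | 2.00 | 77.2% |
| 1 | 0.11 | 1.85 | 0.21 | 1.84 | 83.9% |
| 1 | 0.3 | 2.06 | 0.62 | 1.96 | 78.7% |
| 1 | 0.5 | 2.30 | 1.15 | 1.99 | 77.5% |

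The worst case is slope 1, where baseline explains none of the change and one degree of freedom is spent: 79.6 − 77.2 = 2.4 points lost. The best case in the table gains 95.2 − 79.6 = 15.6 points.

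**3. Residual baseline imbalance.** Under simple randomisation the baseline difference between arms has SD s0·√(2/11), which is 0.43 to 0.64 points. A one-SD imbalance shifts the change-score contrast by (1 − slope) times that: 0.21 to 0.32 points at slope 0.5, and zero at slope 1. Stratifying on pain band makes this smaller.

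**4. Type I error of an unadjusted test after effective stratification.** Take a two-level stratum of equal halves that shifts change by d points. The between-stratum variance is d²/4. The model SE is too large by √(total variance/within-stratum variance), so the effective critical value is roughly 2.086 times that ratio on 20 df.
- d = 2, within-stratum SD 2: √(5/4) = 1.118, critical value 2.33, type I error about 3.0%. With total SD held at 2: √(4/3) = 1.155, critical value 2.41, about 2.6%.
- d = 1, within-stratum SD 2: √(4.25/4) = 1.031, critical value 2.15, about 4.4%.

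Simulations under slightly different set-ups gave about 2.5% to 2.9% for a 2-point shift and 4.4% to 4.7% for a 1-point shift. Blocking on pain band alone, with baseline SD 1.5, gave 4.2% at slope 0.5 and 2.9% at slope 0.2. The shifts and slopes are assumptions.

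**5. Why not adjust for every stratum.** Four medication classes by two pain bands make 8 cells, or 22/8 = 2.75 patients per cell. Adjusting for all of them leaves about 13 df. Counting the lost degrees of freedom alone, power falls to 77.3% if the strata explain nothing.

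**The case against.** The strongest reply is that baseline is already used: it is a Friedman time point, the signed-rank comparator and the reference for response. That stands, and a reader who inferred that the plan ignores baseline NRS would be wrong. These uses remove an additive baseline difference. They do not remove regression to the mean, and they are not a covariate adjustment between arms.

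A reader might also infer that the precision bought by stratification is thrown away, or that the unadjusted test invites false positives. Neither follows. Balance lowers the true variance whatever the analysis; what is lost is its recognition in the SE and the test. The resulting error is conservative.

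The 95% power is tempting to quote alone. It needs a correlation of 0.11 at the top of the baseline SD range, which is low for pain required to have lasted more than 3 months. The SD of change of 2 is itself the plan's conservative value.

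The medication rationale concerns response to Scrambler, which is effect modification. A main-effect medication term would not address it.

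Finally, the Friedman test compares time points within patients and offers no between-arm contrast to adjust. That is a separate and larger defect. It does not dispose of this one, because replacing Friedman with an unadjusted t-test or Mann-Whitney test on change would leave the same gap.

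**Conclusion.** The point holds as a modest one about efficiency and specification. Neither stratification factor enters any Scrambler-versus-sham pain analysis, and baseline NRS is not a covariate in one. Adjusting for baseline NRS would move power from 79.6% to somewhere between about 77% and 95%. Gains are modest or nil at moderate correlations, and the loss is at most about 2.4 points for the baseline term. Ignoring the strata makes an unadjusted test mildly conservative, with type I error of about 2.5% to 4.7% for assumed shifts of 2 to 1 points.

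These figures rest on the plan's SDs, on an assumed two-sided 5% level, and on a correlation and stratum shifts that the document does not give. Pain is a secondary endpoint, although effectiveness is named in the primary objective and the sample size rests on the pain change. The feasibility and acceptability analyses are untouched.

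**What to change.** State that the Scrambler-versus-sham comparison of end-of-treatment NRS, and of the 30- and 60-day scores, is an ANCOVA on arm with baseline NRS as a continuous covariate, and report the adjusted mean difference with its 95% CI. Continuous baseline NRS also largely covers the pain-band factor, and the model supplies the between-arm contrast that the power statement implies.

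One binary pain-medication term is optional. It costs a further degree of freedom and does not deal with effect modification. Do not fit all eight cells.

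If the block sizes and the coding of overlapping drug classes are on record, a p-value from re-randomisation within the strata actually used can be added. The document gives neither.

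The cost is a few sentences in the analysis plan and a few lines of code, with no new data, and at worst about 2.4 points of power for the baseline term. The document describes enrolment in the past tense, so if outcomes had been seen before the change, the adjusted analysis should be labelled post hoc.

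### Overlapping medication levels and eight strata for 22 patients leave only partial balance, and the pain analysis uses neither stratification factor

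*Combined protocol and SAP*

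**What the plan says.** The combined protocol and SAP covers this point in four places.

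- **Participants** (eligibility): "Patients were eligible to use any combination of standard of care medications for pain treatment, including anti-epileptic, antidepressant, opioid or non-steroidal" anti-inflammatory drugs. Four classes are named, and a patient may be on several.
- **Randomization and Masking** (scheme): "Recruitment was batched using a randomized block design", with 1:1 allocation and two factors, "stratifying across medication class (anti-epileptic, antidepressant, opioid or none) and pain level at screening (moderate 4-6, or severe 7-10". The aim is "to promote similar distributions across groups in this small study". Medication was chosen because limited data suggest that "response to Scrambler therapy may differ due to interference of medications used for pain". Block size is not stated. Nor is there a rule for patients on more than one class.
- **Statistical analysis** (pain): NRS scores are analysed with Friedman's test over the four time points and Wilcoxon signed-rank tests against baseline. Neither stratification factor appears in these tests.
- **Statistical analysis** (baseline): demographic and clinical characteristics are compared between arms, without naming drug classes.

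**The concern.** A stratification factor should place each patient in exactly one level. Here a patient on an anti-epileptic plus an opioid fits two levels, so someone must choose. Whichever class is not chosen is balanced only indirectly. That matters because the plan's reason for stratifying is that these drugs may alter response.

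Separately, eight strata among 22 patients leave many blocks incomplete, so some imbalance on both factors is expected. The usual remedy is to carry the factors, or at least the prognostic one, into the analysis. The plan does not do so for pain. Leftover imbalance in screening pain then stays in the between-arm comparison, and the standard error ignores the balance that stratification did achieve.

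**Working it through.** **1. The plan's own figure.** Inputs from Statistical analysis: 11 per arm, a 2.5-point change, SD of change up to 2, 80% power. Two-sided alpha of 0.05 is assumed. n per arm = 2 x (1.960 + 0.842)^2 x 2^2 / 2.5^2 = 10.05, rounded up to 11. Power at 11 per arm is 83.4% by normal approximation and 79.6% by noncentral t. The figure reproduces and does not depend on this point.

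**2. Overlap.** Three classes in any combination give 2^3 = 8 profiles for four levels. Four of the eight profiles contain two or more classes and so fit more than one level.

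**3. Sparsity.** 4 x 2 = 8 strata; 22/8 = 2.75 patients each. In simulation with equal classes, on average 4.0 strata end with an incomplete block of 2, or 6.2 with an incomplete block of 4.

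**4. Balance if each patient took one class.** Simulation of 6,000 trials of 22 patients, assuming equal class shares and 50% severe pain. Entries in the first two columns are mean absolute arm differences in patients.

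| Scheme | Within a class | Among severe pain |
|---|---|---|
| Unstratified 11:11 list | 1.59 | 1.86 |
| 8 strata, blocks of 2 | 0.75 | 1.10 |
| 8 strata, blocks of 4 | 1.02 | 1.46 |
| 8 strata, blocks of 6 | 1.29 | 1.85 |

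The reduction within a class is 1 - 0.75/1.59 = 53% with blocks of 2, 36% with blocks of 4 and 19% with blocks of 6. Balance on pain level improves with blocks of 2 or 4, but hardly at all with blocks of 6.

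**5. Balance with combinations.** The documents give no prevalence, so two settings are assumed. Entries are mean arm differences for the first, second and third listed class.

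| Scheme | 60/40/30% use (about 40% on two or more) | 50/25/25% use (about 25% on two or more) |
|---|---|---|
| Unstratified 11:11 list | 1.83 / 1.85 / 1.69 | 1.89 / 1.64 / 1.59 |
| Filed under first listed class, blocks of 2 | 0.76 / 1.65 / 1.65 | 0.76 / 1.36 / 1.47 |
| Filed under first listed class, blocks of 4 | 0.99 / 1.77 / 1.76 | 0.99 / 1.51 / 1.61 |
| Filed arbitrarily, blocks of 2 | 1.49 / 1.51 / 1.40 | 1.29 / 1.25 / 1.22 |
| Filed arbitrarily, blocks of 4 | 1.70 / 1.68 / 1.60 | 1.49 / 1.41 / 1.42 |

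With arbitrary filing and blocks of 2, the reduction is 17-19% in the heavier-use setting (for example 1 - 1.49/1.83 = 19%) and 23-32% in the lighter one. With blocks of 4 it is 5-9% and 11-21%. Filing under the first listed class protects that class and leaves the other two near the unstratified values.

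**6. Ignoring screening pain in the analysis.** Assume a residual SD of 2, half the patients severe, and a 1.5-point difference in change between pain levels. Adjusted for pain level, the SE of the arm difference is about 2 x sqrt(2/11) = 0.853. Unadjusted, the variance is 4 + 1.5^2 x 0.25 = 4.5625, so the SE is about sqrt(4.5625) x sqrt(2/11) = 0.911. In simulation under the eight-stratum scheme, the unadjusted SE averages 0.90, while the estimate actually varies with SD 0.86. The adjusted SE averages 0.85. Thus 0.90/0.86 = 1.05 (unadjusted error bars about 5% too wide) and 0.85/0.90 = 0.94 (about 6% narrower after adjustment). Monte Carlo error and block size can move these by about 0.02, so only the direction and rough size should be relied on. They describe a linear model for change and are illustrative for rank tests.

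**The case against.** Several stronger readings are tempting, and the documents do not support them.

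- *The scheme cannot deliver balance.* The stated aim is only to promote similarity. With one class per patient, eight sparse strata roughly halve within-class imbalance (blocks of 2), and they also improve balance on pain with blocks of 2 or 4.
- *Most blocks never fill.* This depends on an unstated block size. With blocks of 2, about 13 open and 9 fill; with blocks of 4, only 2.4 of 8.6 fill.
- *NSAID-only patients have no stratum.* That holds only if *none* means no pain medication at all. It can equally mean none of the three named classes, which makes the factor exhaustive.
- *Arm sizes are at risk.* A 13:9 or worse split would be expected in about 12% of trials (blocks of 2) or 24% (blocks of 4), but the document reports "We enrolled 22 patients with NMOSD (11 per arm". That risk did not materialise, although equal arms do not show balance within classes.
- *Collapse medication to any drug yes/no.* This gives four strata and steadier arm sizes, but the within-class difference becomes 1.51-1.55, close to the unstratified 1.58-1.60. It gives up the class balance that was the purpose.

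It is also fair that effectiveness is a secondary endpoint, that a baseline comparison is planned, and that batched recruitment may not behave like independent permuted blocks. What remains is the overlap, which is plain in the text, and the absence of both factors from the pain analysis.

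**Conclusion.** The concern holds in a limited form. The medication levels overlap for patients whom the eligibility criteria expressly admit, and the scheme gives partial balance on medication class and pain level. Under the assumptions shown, the reduction in class imbalance ranges from 53% (one class each, blocks of 2) to 5-9% (about 40% combination users, arbitrary filing, blocks of 4). The documents give neither the prevalence nor the block size needed to locate the trial in that range.

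The consequence that can still be corrected is in the analysis. Leaving out screening pain makes the between-arm error bars about 5% too wide and leaves chance imbalance uncorrected, if pain level shifts change by 1.5 points. A smaller effect would mean a smaller gain. This is a modest improvement at almost no cost. It does not invalidate the randomization or the sample size.

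**What to change.** In the between-arm comparison of NRS change, account for screening pain, using either the two-level stratum or the score itself. A stratified rank test (van Elteren) or ANCOVA on change would serve. Friedman's test ranks within patients, so it cannot carry this adjustment; the comparison of change between arms has to be named explicitly.

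Tabulate each drug class, including NSAIDs, as a separate yes/no indicator by arm. Medication is better tabulated than modelled, because eight overlapping profiles are too many for 22 patients.

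The cost is one extra model term (residual degrees of freedom fall from 22 - 2 = 20 to 22 - 3 = 19) and one table from data already needed for randomization. Because the document describes enrolment as complete, report the adjusted result beside the planned tests and label it as added if pain outcomes had already been seen. A sentence giving the block size and the filing rule used would let readers judge the balance, but the fix does not depend on it.

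### The only treatment guess described is taken after the ten-session course, so an effective treatment can look like failed masking

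*Combined protocol and SAP*

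**What the plan says.** All references are to the combined protocol and SAP.

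- **Study objectives and measures.** One feasibility measure is "response to the following question asked directly after completion of the 10-day treatment period: 'Do you think you received treatment?' (Yes/No". Feasibility is part of the primary outcome and is meant to inform a Phase III study. No other time point for the guess is given.
- **Same section, design.** "we performed a randomized single blind, sham-controlled trial testing Scrambler therapy in patients with NMOSD".
- **Same section, pain ratings.** "Prior to initiation of Scrambler therapy and at completion of treatment, patients were asked to rate their pain by the 11-point NRS score". The order of the final rating and the guess is not stated.
- **Randomization and Masking.** Within a Scrambler session, "pain was assessed by asking the patient how s/he felt in the area of pain covered by the electrodes", and the stimulation is adjusted to the answer.
- **Statistical analysis.** The guess is used twice. First: "For each of the two survey questions used to assess feasibility and acceptability, as described above, a 95% confidence interval" is calculated for the proportion answering Yes. Second, a chi-squared test sets the Yes count among Scrambler patients against the sham count: "the number of sham patients who thought they received treatment was performed to determine if masking was effective".
- **Statistical analysis, sample size.** With 11 patients per arm, "we were able to detect a change of 2.5 points in the Scrambler group at 80% power, with a difference in proportions of 60" percent between the arms. A responder is defined by a fall of 1.80 NRS points from baseline to end of treatment.

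The documents mention no earlier guess, no reason for or certainty of the guess, and no analysis of the guess by pain response.

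**The concern.** A between-arm difference in guesses tells us about masking only if nothing else that differs by arm drives the guess. At the end of the course, pain relief may do so. A patient whose pain has fallen has a reason to answer Yes, and one whose pain has not has a reason to answer No, whatever the device felt like. If Scrambler works, relief differs by arm, and the guesses can then differ by arm with a perfect sham.

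The reverse path is also open. Electrical stimulation and motor vibration may feel different, and a patient who recognises the real device may report more relief. One Yes/No answer at the end cannot separate these two explanations.

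At stake is how the sham is judged. The test described is the only masking check, and the same answer feeds the feasibility assessment for Phase III. A sound sham could be written off, or a real masking problem explained away. This concerns what the answer measures, not the size of the trial: with more patients, the confounded test would reject more often.

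**Working it through.** **1. The plan's own figure.** Inputs from the sample-size paragraph: difference 2.5, SD of change 2, 11 per arm, 80% power. No alpha is stated; two-sided 5% is assumed.

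n per arm = 2(1.960 + 0.842)² × 2² / 2.5² = 10.05, rounded up to 11. Power with 11 per arm is 83.4% by the normal approximation and 79.6% by the two-sample t-test. The stated figure reproduces when the change is read as a between-arm difference. The concern does not affect it.

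**2. Responder rates.** Assume normally distributed changes with SD 2 and the 1.80-point threshold. Φ is the standard normal distribution function.

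- Scrambler, mean fall 2.5: 1 − Φ((1.80 − 2.5)/2) = Φ(0.35) = 63.7%.
- Sham, mean fall assumed 0: 1 − Φ(1.80/2) = 1 − Φ(0.90) = 18.4%.
- Sham, mean fall assumed 1: 1 − Φ((1.80 − 1)/2) = 1 − Φ(0.40) = 34.5%.
- Alternative: read the 60% difference as responder rates, assumed 80% against 20%. The plan gives no base rates and does not say what the proportions are.

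**3. Guess model with intact masking.** The guess depends on response and never on arm. With r the responder rate in an arm:

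P(Yes) = r × P(Yes | responder) + (1 − r) × P(Yes | non-responder).

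Example, 90% of responders and 10% of non-responders answering Yes (90/10), sham change 0:

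- Scrambler: 0.637 × 0.9 + 0.363 × 0.1 = 0.609.
- Sham: 0.184 × 0.9 + 0.816 × 0.1 = 0.247.

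**4. Probability of a significant masking test.** This is an exact enumeration of two binomials of size 11, counting tables with p < 0.05. The plan does not say whether a continuity correction applies, so each cell gives the Pearson result, with the corrected result in brackets.

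| Yes among responders / non-responders | 63.7% vs 18.4% (sham change 0) | 63.7% vs 34.5% (sham change 1) | 80% vs 20% (60-point reading) |
|---|---|---|---|
| 100/0 | 61% (42.5%) | 29% (16%) | 87% (73%) |
| 90/10 | 42% (25%) | 20% (10%) | 66% (48%) |
| 80/20 | 26% (13%) | 13.5% (6%) | 41% (25%) |
| 90/50 | 13.5% (6%) | 8% (3%) | 21% (11%) |
| 50/50 (guess unrelated to response) | 5.3% (1.7%) | 5.3% (1.7%) | 5.3% (1.7%) |

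Every significant result in this table is a false alarm, because masking is intact by construction.

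**5. Size of the cells in a table by response.** With responders at 80% and 20%, the expected number of Scrambler non-responders is 11 × 0.2 = 2.2, and of sham responders also 11 × 0.2 = 2.2. With 63.7% and 18.4%, they are 11 × 0.363 = 4.0 and 11 × 0.184 = 2.0.

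**The case against.** A reader might infer that an effective treatment will necessarily fail this masking test. The documents do not support that. It would need guesses to follow relief closely and sham patients to improve little, and neither quantity is given. In the weakest case above the false-alarm rate is 8%, close to the benchmark. The highest figures rest on the 80% against 20% split, which is an assumption about an undefined 60% difference.

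A reader might also infer that masking did fail, or that the pain comparison is biased. Nothing in the documents shows either. The point is that this check could not tell.

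A third inference would be to replace the final guess with one after session 1. That is a trade-off. Patients are asked about their pain within Scrambler sessions, so even an early guess may reflect relief. It would also miss unmasking in sessions 2 to 10, and masking at the end of the course is what bears on the end-of-treatment pain score.

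Three further objections stand in part:

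- No decision rule or effectiveness analysis depends on the masking test, so the harm is one of interpretation.
- The text describes enrolment as done, so an early question may no longer be possible in this cohort.
- The table by response will be too sparse to settle the direction of cause.

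That the guess is taken only once is inferred from the absence of any other time point. That the order of the final NRS rating and the guess is unstated matters little, since patients feel their own pain.

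**Conclusion.** The concern holds as a limit on inference. The plan states that a between-arm chi-squared on the end-of-course guess determines whether masking was effective, and nothing in the plan separates perceived relief from loss of masking. With intact masking and 11 per arm, the chance of a significant result is 13.5% to 61% (Pearson; 6% to 42.5% corrected) with the plan's 2.5 points, SD 2 and 1.80 threshold. It is 8% to 29% (3% to 16%) with a 1-point sham improvement, and 21% to 87% (11% to 73%) on the 80% against 20% reading. The benchmark is 5.3% (1.7%). The ranges rest on assumed guess behaviour, an assumed sham change, normality and a two-sided 5% level. The conclusion that the test can mislead needs only that relief differs by arm and that guesses depend to some degree on relief.

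**What to change.** **For the data already specified.** Keep the end-of-course guess and its confidence interval. Add a table of the guess by arm, separately for patients who did and did not reach the 1.80-point response. Label it descriptive, since two of the four arm-by-response groups may hold about 2 patients each. State that a significant end-of-course chi-squared will not by itself be read as failed masking. This costs one table and one sentence, with no new data.

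**Where sessions are still to be run, or in the Phase III study.** Ask the same Yes/No question after session 1, with the main reason (sensation, change in pain, other), alongside the end-of-course question and not in place of it. Report both by arm. This costs one short question at an existing visit. It may make patients think about allocation sooner, and it reduces the problem without necessarily removing it, because pain feedback is part of a Scrambler session.
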